## **10.2 Reporting of Adverse Events**

---

o The 2-day timeframe refers to 2 business days from the point at which the Investigator makes the determination that the event is a UADE. This timepoint may be after the point at which the Investigator learns of the event itself.

All adverse events, non-serious and serious, that occur during the study must be reported on the Adverse Event eCRF. The report should include, wherever possible, time of onset, severity, duration, outcome, and the Investigator's medical judgment as to the relationship of the adverse event to the study device, procedure, (i.e. not related, possibly related, definitely related, or relationship unknown).p

All SAEs must be reported to the Sponsor or its CRO within 5 business days of the Investigator's knowledge of the event. The event is reported in the electronic data capture system. IRB notification of the adverse event may also be required, depending on the conditions of approval or requirements of the respective committee. Any UADEs must be reported to the Sponsor/CRO within 1 working day from when the Investigator first learns of it.

Non-serious reportable adverse events are to be submitted via the EDC in a timely fashion. Certain reportable events may require adjudication; therefore, supporting documentation must be sent to the Sponsor/CRO upon request.

Events that occur before consenting of the patient are not reported. Adverse events that occur after consenting in patients that are screen fails, in other words, in those for whom the Investigator decides not to treat with the study device (Lava LES) will also not be reported. Adverse events that occur after consenting of the patient in enrolled subjects (i.e. those for whom the Investigator decided to treat with the study device) will not be reported if they occur prior to the start of the index procedure (defined as the beginning of arterial access; see **Section 6.5**, above), but will be reported as procedure-related adverse events if they occur after the start of the index procedure but before Lava is administered into the delivery catheter.

Events related to preexisting conditions are not reported unless there is worsening of the condition after enrollment (or after the start of the index procedure, as specified in the paragraph above).

Reinterventions are not reported as adverse events; rather, the event that prompted the reintervention (for example, rebleeding) is reported as the adverse event and the reintervention is reported as an outcome of that event.

### **10.3 Independent Medical Monitor**

The independent Medical Monitor will be a board certified or board eligible licensed physician independent from the Sponsor. The Medical Monitor will be trained to the Protocol, a Safety Plan (if one is utilized) and the CEC Charter. The Medical Monitor will review every adverse event and device deficiency in the study. Adverse events will be classified as to seriousness, relatedness, whether they

---

p Each adverse event will be reviewed by the independent Medical Monitor for seriousness, relatedness, and whether it is anticipated. Certain events, as specified in the CEC Charter, will also undergo adjudication by the CEC. If the Investigator and the Medical Monitor disagree on an element of an adverse event, the Medical Monitor's classification will prevail for endpoint reporting purposes. If the CEC classification differs from that of either the Investigator or the Medical Monitor, the CEC classification will prevail.

are anticipated, and whether they meet a trigger for CEC adjudication, as specified in the CEC Charter. The Medical Monitor will re-review adverse events where new information has been reported. The Medical Monitor will determine whether re-adjudication is necessary, based upon new information.

#### **10.4 Clinical Events Committee**

The CEC will be comprised of independent physicians who are not participants in the study. The CEC is charged with the development of specific criteria used for the categorization of clinical events and clinical endpoints in the study which are based on the Protocol. All members of the CEC will be blinded to the primary results of the trial. The CEC will review and adjudicate appropriate clinical events on a regular basis. The events requiring adjudication will include those related to the device and to the primary safety and effectiveness endpoints, guided by a CEC charter.

#### **10.5 Data Safety Monitoring Board**

The Data Safety Monitoring Board (DSMB) will be responsible to ensuring that the study is being conducted ethically and to adjudicate all possibly and definitely device- and/or procedure-related serious adverse events. The DSMB membership is represented from the key medical disciplines involved with the study procedure and may include an external biostatistician. None of the members may be directly involved with the clinical trial. The Sponsor has contracted a Clinical Research Organization to organize, facilitate, and document meetings for the DSMB for this trial. The DSMB will meet regularly and as necessary, guided by the DSMB Charter.

### **11 DEVICE ACCOUNTABILITY**

#### **11.1 Accountability and Procedures**

1. Each device shipment must be documented on the Device Accountability Log and include the receipt, dispensing, and return of investigational devices.
2. When a shipment is received, the Investigator (or designee) must record on the Device Accountability Log the date received and the Catalog and Lot Number of each device. It is recommended that the Packing List also be signed and dated.
3. Investigational devices must be kept in a secure, limited access storage area under recommended storage conditions (room temperature).
4. During the study, the following information must also be noted on the Device Accountability Log:
  - Identification number of the subject for whom the device was intended
  - Procedure date

5. The Device Accountability Log must be readily available for inspection by representatives from the Sponsor, the IRB, and/or other relevant regulatory authorities at any time.
6. The Device Accountability Log and device storage locations will be reviewed during monitoring visits.
7. All unused investigational devices must be returned to the Sponsor once it is determined they will not be used. Upon completion of the study, all unused investigational devices must be returned to the Sponsor if any remain at the site. The monitor must verify return at the close out visit, or before.

## 12 STUDY ADMINISTRATION

### 12.1 Site Initiation

A Site Initiation Visit (SIV) will be conducted by the Sponsor or other appropriate designee, for example, its CRO, to ensure that all study supplies are present, to ensure proper training of the Investigator and study staff members in study-specific procedures, to ensure regulatory requirements are fulfilled prior to enrollment of the first study subject at a site, and to verify the site facilities and equipment are appropriate for conduct of the study.

The following items will be reviewed at the SIV. All training will be documented and must contain signatures of participants:

1. Introduction and overview of agenda;
2. Obligations of the Investigator, including his/her responsibilities to ensure only appropriately qualified staff participate in the study conduct, and notification to the Sponsor or its CRO of any change in staff listed on the Delegation of Authority (refer to the site's Regulatory Binder) during the course of the study;
3. Protocol (overall review including, but not limited to, inclusion/exclusion criteria, recruitment/withdrawal of subjects, study restrictions);
4. Completion and maintenance of the Delegation of Authority;
5. Adverse experience reporting and unanticipated adverse device effect (UADE) reporting;
6. eCRFs (procedures, corrections, timely completion, retention);
7. Source document preparation and retention;
8. Role of the IRB;
9. Informed Consent process;

10. Study file documents and document retention (ensure all pertinent regulatory documents are collected prior to the site starting the study);
11. Clinical supplies and device management (storage and accountability; device dispensing, labeling, and packaging);
12. Clinical laboratory facilities;
13. Requirements for reporting any clinical data back to the Sponsor. (e.g., annual and final reports);
14. Monitoring schedule/plan;
15. Other items that should be discussed: background and purpose of the study, previous studies/data, regulatory requirements, policy for publishing trial results, any special equipment required.

## **12.2 Clinical Site Monitoring**

Interim monitoring will be conducted by the Sponsor or designees (e.g. CRO) to ensure compliance with standard operating procedures (SOPs), the Protocol, and other written instructions and regulatory guidelines.

The study monitor is the primary liaison between the Sponsor and the Investigator. The main responsibilities of the monitor are to visit the Investigator before, during, and after the study to ensure adherence to the Protocol; to verify all data are correctly and completely recorded and reported; and confirm that informed consent is obtained and recorded for each subject before study participation.

The study monitor will contact and visit the Investigator at regular intervals throughout the study, as guided by the study Monitoring Plan. The monitor will be allowed to check and verify the various records (eCRFs and other pertinent source data records) relating to the study to verify adherence to the Protocol and to ensure the completeness, consistency, and accuracy of the data being recorded.

As part of the supervision of the study progress, other Sponsor personnel may accompany the study monitor on visits to the study center. The Investigator and research staff must agree to cooperate with the study monitor to resolve any problems, errors, or possible misunderstandings concerning the findings detected in the course of monitoring visits.

## **12.3 Study Termination**

The Sponsor and applicable regulatory authorities have the right to terminate the entire study or an investigational site at any time. The DSMB may recommend study termination to the Sponsor, but the Sponsor holds the ultimate responsibility and authority for termination in this regard. If the Sponsor chooses not to follow the DSMB's recommendation for study termination, the circumstance underlying this decision must be reported to the IRBs and the FDA.

Situations that could warrant study termination include, but are not limited to:

1. Increased incidence of adverse experiences and/or the severity of such, suggestive of a potential, device-related health hazard;
2. Insufficient subject enrollment;
3. Recurrent protocol non-compliance, violations or deviations;
4. Inaccurate, incomplete, and/or untimely data recording, on a recurrent basis;
5. Lack of cooperation with monitoring visits (e.g., failure to adequately prepare for visits, address action items from one visit to the next, or provide access to medical records).

## **12.4 Data Handling and Recordkeeping**

### **12.4.1 Completing, Signing and Archiving Case Report Forms**

The Investigator must keep a separate subject identification list showing enrollment numbers, names, and dates of birth to allow unambiguous identification of each subject included in the study. It is recommended a note be made in the medical record that the subject is participating in a clinical research study.

The required data will be recorded on the eCRFs. A web-based EDC will be used to record and manage study data. eCRF completion guidelines, the instructions for electronic data entry, will be developed in conjunction with the Sponsor, the CRO, and/or the EDC vendor. The eCRFs will be completed electronically, with reasons documented for missing data. All eCRFs must be kept in good order and updated so they always reflect the latest observations on the subjects participating in the study.

The Investigator will sign the appropriate screens of the eCRF and source documentation. eCRF corrections will be made electronically and signed electronically by the Investigator. An embedded audit trail will capture the date, time and user making updates and changes to the electronic data.

Because it is important to have proper data collection in a timely manner, within 2 business days, the Investigator/Study Coordinator shall complete the eCRFs and provide them to the monitor upon request. When the monitor requests additional data or clarification of data for the eCRF, the request must be answered satisfactorily before the next monitoring visit.

### **12.4.2 Data Management and Archiving**

The Sponsor will be responsible for the processing and quality control of the data. Source data for safety will be retained for at least 2 years after the termination/completion of the study or after the approval/withdrawal of the marketing application, whichever occurs later. All other source data, eCRFs, copies of Protocols and protocol amendments, device accountability forms, correspondence, subject identification lists, informed consent forms, and other essential documents must be retained for a period of at least 2 years after the last approval of the marketing application and until there are

no pending or contemplated marketing applications, or at least 2 years have elapsed since the formal discontinuation of clinical development of the investigational device. The Sponsor will inform the Investigator/ Institution when these documents are no longer required to be retained.

No study document or image will be destroyed without prior written agreement between the Sponsor and the Investigator. Should the Investigator wish to assign the study records to another party or move them to another location, advance written notice must be given to the Sponsor.

#### **12.4.3 Direct Access to Source Data**

The Sponsor, auditors, and health authority inspectors (or their agents) will be given direct access to source data and documentation (e.g., medical charts/records, laboratory test results, printouts, videotapes) for source data verification, provided that subject confidentiality is maintained in accordance with local requirements.

The Investigator must maintain the primary records, (i.e., source documents) of each subject's data. Examples of source documents are hospital records, office visit records, examining physician's findings or progress notes, consultant's written opinion or notes, laboratory reports, device inventory, device label records, and eCRFs that are used as the source.

The Investigator will maintain a confidential subject identification list that allows the unambiguous identification of each subject with cross-referencing of the unique subject identifier and the subject's name and other identifying information (e.g. date of birth). The confidential subject identification list will be retained at the site. All study-related documents must be retained by the investigational site until notification by the Sponsor.

### **13 ETHICS**

#### **13.1 Informed Consent**

Written informed consent must be obtained for each subject before any study-specific procedures or assessments are done and, specifically, prior to the subject being treated with the Lava LES. Written informed consent will be obtained after the aims, methods, anticipated benefits, and potential hazards are explained.

If required by institutional policy, informed consent will be obtained prior to review of Baseline and Screening data. A Screening Consent Form may also be available to secure permission from the subject for reviewing prospective subject information (if requested/required by site or IRB policy) prior to the subject agreeing to participate in the trial and signing the study-specific Informed Consent Form.

The subject's or their Legally Authorized Representative's willingness to participate in the study will be documented in writing in a study-specific Informed Consent Form, which will be signed and dated by the subject or their Legally Authorized Representative and a witness. The Investigator will keep the original consent form and a copy will be given to the subject. It will be explained to the subjects that they are free to refuse entry into the study and free to withdraw from the study at any time without prejudice to future treatment. Subjects will be consented for 3 years to allow for the ability to collect additional data, if initial study results indicate a need for additional long-term information (i.e., during the post-approval phase).

### **13.2 Institutional Review Board**

This study must be approved by an appropriate IRB at each investigational site. Securing the approval is the responsibility of the Investigator, as defined by ISO 14155-1 and FDA regulations (21 CFR Part 56) prior to starting the study. The Sponsor must receive a copy of the IRB approval letter (or equivalent documentation) for the Protocol and Informed Consent Form before the study can be started at that site or devices shipped to that Investigator.

The IRB and Sponsor must approve any significant changes to the Protocol as well as a change of Principal Investigator. Documentation of the IRB approval must be provided to the Sponsor. Records of all study review and approval documents must be maintained by the Investigator in the Regulatory Binder and are subject to inspection by the Sponsor or regulatory authority during or after completion of the study. Serious Adverse Events and deaths must also be reported to the IRB and Sponsor (reference **Section 10** for reporting instructions).

The Investigator must notify the IRB, as per their reporting guidelines, and the Sponsor when he or she deviates from the Protocol. The Sponsor must be notified of all relevant action taken by the IRB and must receive a copy of all study-related correspondence between the Investigator and the IRB.

The IRB must receive notification of the completion of the study and final report within 3 months of study completion or termination. A copy of these reports must be provided to the Sponsor. The Investigator must maintain an accurate and complete record of all submissions made to the IRB, including a list of all reports and documents submitted.

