##### **6.6.1 Screen Fails**

Patients who are consented but who, for whatever reason, are not enrolled (e.g., they do not meet the eligibility criteria after diagnostic angiography) will be considered screen failures and will be not be followed further. The reason for excluding these subjects from enrollment will be documented in the Electronic Data Capture (EDC) system.

---

f If the Investigator believed at the time of diagnostic imaging that 4 or fewer lesions required embolization but, during the course of treatment it is in the subject's best interest to embolize more than 4 lesions, the additional lesions must be treated with non-study agents/devices. Any complications related to the additionally embolized lesions will be considered procedure-related but not device-related events. Rebleeding documented to be from the additionally embolized lesions will not trigger the primary effectiveness endpoint.

g Provocative angiography may be performed at the Investigator's discretion. Complications from provocative angiography are considered procedure-related but not device-related events.

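### Protocol safety-reporting rules conflict on IRB notification and on UADE timing, and they can leave serious procedural harm unreported when Lava is not used

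*Protocol*

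**What the plan says.** **IRB reporting.** Protocol Section 13.2 says "Serious Adverse Events and deaths must also be reported to the IRB and Sponsor" and sends the reader to Section 10 for instructions. Section 10.2 says "IRB notification of the adverse event may also be required, depending on the conditions of approval or requirements of the respective committee".

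**Events without Lava.** Section 10.2 takes "Adverse events that occur after consenting in patients that are screen fails" and says they are not reported. It describes these patients as those whom the Investigator decides not to treat with the device, and it makes no exception for serious or fatal events. Section 6.5 adds to the screen fails any consented patient whose index procedure is performed but in whom the Investigator decides at that procedure not to use Lava. Section 6.6.1 ends their follow-up. A footnote to that rule in Section 6.5 states: "Complications from provocative angiography are considered procedure-related but not device-related events". For enrolled subjects whom the Investigator decided to treat, Section 10.2 does require events between the start of arterial access and Lava administration to be reported as procedure-related.

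**Timing.** Section 10.1 gives 2 business days for a UADE, and footnote o starts that clock when the Investigator determines that the event is a UADE. Section 10.2 gives 1 working day from first learning of it. For SAEs, Section 10.2 says "All SAEs must be reported to the Sponsor or its CRO within 5 business days of the Investigator's knowledge of the event", and "The event is reported in the electronic data capture system". Section 12.4.1 separately says that "within 2 business days, the Investigator/Study Coordinator shall complete the eCRFs".

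**The concern.** The cross-reference in Section 13.2 leads from an obligation to a possibility, so it settles nothing. With up to 20 sites (Section 6.1), two sites could treat the same SAE differently and each point to a protocol section in support.

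The exemption for screen fails matters more. The index procedure begins at arterial access (Section 8.2), and provocative methods are allowed. A patient can therefore be seriously harmed by a study-period procedure before any Lava is given. If the harm is the reason Lava is not used, the event itself can move the patient into the group whose events are not reported. Whether an event is recorded would then depend on its consequences, and the missing events would tend to be the serious ones.

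The Medical Monitor is to review every adverse event (Section 10.3), and the DSMB is to adjudicate procedure-related SAEs (Section 10.5). Neither can assess what is never reported. Section 3 says that Lava has had no prior investigations, so there is no earlier safety record to fall back on.

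**Working it through.** No sample size, power or event count is involved. The check sets the rules side by side.

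**1. IRB recipient.** Reporting to the Sponsor is mandatory in both sections, so the conflict concerns the IRB only.

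| Section | SAE to IRB | Time limit to IRB |
|---|---|---|
| 10.2 | conditional on the committee | none |
| 13.2 | mandatory; also names deaths | none; defers to Section 10 |

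Deaths do have a rule in Section 10. Section 10.1 lists a fatal outcome among the SAE criteria, so a reportable death falls under the SAE rule in 10.2.

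**2. Which events are reported.** Four cases, all in consented patients after arterial access:

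| Case | Rules that apply | Reported? |
|---|---|---|
| A. Harm before any decision to use Lava; Lava not used | 6.5: screen fail. 8: not enrolled. 10.2: exempt | No |
| B. Decision to use Lava made; complication before administration; Lava abandoned | 8: enrolled, so the pre-Lava sentence in 10.2 applies. 6.5: screen fail, so the exemption in 10.2 applies. 8.8: an aborted procedure keeps its roster position, as for an enrolled subject | Unclear |
| C. Complication before administration; Lava then given | 10.2: procedure-related event | Yes |
| D. Complication after Lava is given | 10.2: adverse event | Yes |

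Case B is unclear because enrollment is defined twice. Section 6.5 enrolls at access to the Target Lesion, then reclassifies the patient if Lava is not used. Section 8 enrolls at the decision to use Lava. The two sentences in Section 10.2 separate patients by the Investigator's decision but do not say what happens when that decision is reversed.

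**3. UADE clocks.** Let d be the number of business days from first learning of the event to determining that it is a UADE.

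- Section 10.1 with footnote o: due d + 2 business days after first learning.
- Section 10.2: due 1 working day after first learning.
- Difference: (d + 2) − 1 = d + 1 business days.

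With d = 0 the two limits differ by 1 day. Any delay in the determination widens the gap.

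**4. SAE limit and eCRF rule.** Section 10.2 puts all adverse events on the Adverse Event eCRF and allows up to 5 business days for an SAE. Section 12.4.1 gives 2 business days for eCRFs in general, states no starting point and does not mention SAEs. A site that enters the event within 2 business days of learning of it satisfies both. The tension is indirect.

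**The case against.** The strongest reply is that the exemption is a deliberate design choice. Section 10.1 defines an adverse event as one that follows the experimental therapy, so a patient never given Lava has none to report. Section 6.6.1 still requires the reason for exclusion to be documented in the EDC. The footnote on provocative angiography assigns relatedness only; it sets no reporting rule, and it also fits subjects who later receive Lava.

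Part of this stands. The footnote does not by itself contradict Section 10.2. But the definition in Section 10.1 cannot settle the matter, because Section 10.2 itself requires pre-Lava events to be reported in subjects the Investigator decided to treat. A reason for exclusion is not an SAE report.

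On the IRB point, the reply is that Section 13.2 defers to Section 10 and that local IRB rules govern in practice. That makes the repair short, but the two sections still say different things.

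A reader might also infer more than the text supports:

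- *Three rival SAE clocks.* Section 13.2 sets no time limit, and Section 12.4.1 is a general data-entry rule.
- *Non-serious events due before serious ones.* Section 10.2 has its own rule for non-serious events, which asks only for timely submission.
- *No rule for deaths in Section 10.* Deaths are SAEs under Section 10.1.
- *All harm unreported whenever a procedure ends without Lava.* The pre-Lava sentence in Section 10.2 covers subjects the Investigator decided to treat, and Section 8.8 treats an aborted case as that of an enrolled subject.

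**Conclusion.** The point holds in three parts.

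- Sections 10.2 and 13.2 conflict directly on whether SAEs go to the IRB.
- Section 10.2, read with Section 6.5, exempts serious and fatal harm that occurs in the index procedure before any decision to use Lava, if Lava is then not used. When a complication causes Lava to be abandoned after that decision, the protocol supports both reporting and not reporting.
- The UADE clocks in Sections 10.1 and 10.2 conflict directly, by at least 1 day.

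The number of events at stake cannot be estimated: neither document gives an expected count of screen fails or a complication rate for them. A reader might infer that the primary safety result is biased, but the documents do not show this. Most components of the composite require Lava or its delivery catheter, and Section 6.6.2 limits the ITT population to patients in whom the device entered the vasculature. The consequence is for what reaches the Sponsor, Medical Monitor, DSMB and IRBs. The conclusion rests on reading Sections 6.5 and 10.2 as written; site training or the committee charters may be narrower, but they are not among the documents.

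**What to change.** 1. Reconcile Sections 10.2 and 13.2 into one statement on IRB reporting of SAEs and deaths.
2. Reconcile the UADE clocks in Sections 10.1 and 10.2, both length and starting point, and state how the SAE limit in 10.2 relates to the eCRF rule in 12.4.1. Which limits apply is for the sponsor to decide.
3. Align Sections 6.5, 8, 8.8 and 10.2 on when a patient is enrolled and when a patient becomes a screen fail, including the case in which a complication leads the Investigator to abandon Lava.
4. Require SAEs and deaths from the start of the index procedure to be reported in every consented patient, whether or not Lava is used. List screen fails separately, so that the ITT endpoints, performance goals and sample size do not change.

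The cost is protocol wording, a short SAE form for screen fails and slightly more reporting by sites.
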